5.3.9.2 Outliers

Outliers will be identified during data management and data analysis process, but no sensitivity analyses will be done to evaluate the impact of outliers on efficacy or safety outcomes. All data will be included in the data analysis.

5.3.11 Reporting conventions

Vital signs, laboratory and biomarker parameters will be reported in International Units. The descriptive statistics will be reported to 2 decimal places, except for 1) those parameters with low measurements such as biomarkers or others, that will be reported to 3 or 4 decimal places, as appropriate; 2) those parameters not requiring decimal places, will be reported without any decimal place. Estimated parameters, such as regression coefficients will be reported to 3 decimal places. Percentages should be rounded to a single decimal place. P-values ≥0.0001 will be reported to 4 decimal places; p-values less than 0.0001 will be reported as "<0.0001." All reported dates will be shown in YYYY-MM-DD format.

5.3.12 Study timelines

Each patient will participate in the study up to approximately 77 weeks (a 5-week Screening Period, a Day 169 Treatment Period, and a Day 505 Follow-Up Period commencing after the last dose of study medication at Week 20).

A Safety Committee with take place after 7 to 10 days of all ongoing patients in the sentinel cohort have completed the respective dose of study medication and will determine the decision to continue at that dose into the expanded cohort. The DMC scheduled meetings will take place after the 28-day observation period after the 3rd dose of study medication (Day 85) of the first 20 patients and at the conclusion of the trial.

5.3.13 Technical Details

The most updated study protocol has been used as a reference for this document. SAS programs, SAS Logs and SAS outputs generated during the creation of the Statistical Report will be archived in the PIVOTAL's File System.

5.3.14 Software

The statistical analysis will be performed using the scientific software SAS® V9.4 or later releases and SAS® Enterprise Guide V7.15 or later releases.

5.3.15 Database Standardization

Datasets for analyses will follow CDISC compliance. SDTM version will be detailed in the corresponding Specifications document.

5.3.16 Maintaining the Blind during the study

Patients will be unblinded **as necessary** to assess the relationship between the study medication and events that meet criteria for Stopping Rules. Patients who experience events that meet criteria for Stopping Rules will permanently terminate dosing.

If unblinding is required in the interest of the safety of a patient, an Investigator will discuss the matter with the Sponsor before unblinding. In a medical emergency, the Investigator or delegate may unblind via the IWRS for that patient without prior consultation with the Sponsor. In that event, the Investigator or delegate will notify the Sponsor as soon as possible that the randomization code has been broken for the patient. If the blind is broken, the date, time, and reason must be recorded.

Patients may also be unblinded for the processing of SAEs, expedited safety reports, and the emergency unblinding of patients, as detailed in a separate Safety Management Plan.

All statistical analysis will be performed by a blinded team of statisticians and statistical programmers, who will work in a secure area without any treatment identifying information. For the interim analysis the blinded team will handover all programs prepared using blinded information to the unblinded team who will then be able to prepare unblinded outputs required for the interim analysis as specified in Appendix 1.0 of this document.

No unblinded individual level data will be shared with anyone outside the unblinded team. The unblinded team will be defined in the Project Management Plan.

5.3.17 Changes to Protocol-planned Analyses

According to the protocol, ECG parameters will be summarized by treatment group and protocol specified collection time point and a summary of change from baseline at each protocol specified time point by treatment group will also be presented. However, ECG parameters have not been collected and they are not available for analyses.

22-Apr-2024

7. APPENDIXES

Appendix 1.- Tables, Figures, and Listings

Appendix 1.- Index of Tables, Figures, and Listings

TFL Number	Title	Analysis Set	Included in	TOP LINE
			Final report	TABLES
Table Number				
14.1 Demograph	ic Data Summary Tables			
14.1.1 Patient Di	sposition			
14.1.1.1	Patient Enrollment and Disposition	All Screened Patients	Yes	V
14.1.1.2	Patient Study Status	All Screened Patients	Yes	
14.1.1.3	Analysis Populations	Randomized Patients	Yes	
14.1.1.4	Protocol Deviations	mITT Population	Yes	
14.1.2 Demograp	phic and Baseline Characteristics			
14.1.2.1	Demographic Characteristics	mITT Population	Only mITT	V
14.1.2.2	Baseline Characteristics	mITT Population	Only mITT	V
14.1.2.3	Specific Disease Characteristics: Fibroscan,	mITT Population	Only mITT	
	Hepatitis B genotype, HCV, HDV and HIV tests			
	and HBV serology and viral markers			
14.1.2.4	Medical History by System Organ Class and	mITT Population	Yes	
	Preferred Term			
14.1.2.5	Baseline Physical Examination	mITT Population	Yes	
14.1.3 Prior and	Concomitant Medications			,
14.1.3.1	Prior Medication by ATC 1st and 2nd level	Safety Population	Yes	
14.1.3.2	Concomitant Medication by ATC 1st and 2nd level	Safety Population	Yes	
14.1.4 Extent of	Exposure for Investigational Products		'	1
14.1.4.1	Treatment Exposure	Safety Population	Yes	
14.2 Efficacy Da	ta Summary Tables and Figures		'	•

TFL Number	Title	Analysis Set	Included in	TOP LINE
			Final report	TABLES
14.2.1 Primary	Efficacy Endpoint			 
14.2.1.1	Summary of patients achieving Virologic Response	mITT Population	Only mITT	V
	on Day 169			
14.2.1.2	Logistic Regression Analysis for Virologic	mITT Population	Only mITT	V
	Response on Day 169			
14.2.2 Seconda	ry Efficacy Endpoint		•	,
14.2.2.1.1	Summary of patients achieving Serologic	mITT Population	Yes	
	Clearance of HBsAg on Day 169			
14.2.2.1.2	Logistic Regression Analysis for Serologic	mITT Population	Yes	V
	Clearance of HBsAg on Day 169			
14.2.2.2.1	Summary of patients achieving Serologic	mITT Population	Yes	
	Clearance of HBV DNA on Day 169			
14.2.2.2.2	Logistic Regression Analysis for Serologic	mITT Population	Yes	V
	Clearance of HBV DNA on Day 169			
14.2.2.3.1	Summary and change from baseline of qHBsAg,	mITT Population	Yes	
	HBV DNA, HBcrAg and pg-RNA levels: Days 85			
	and 169			
14.2.2.3.2	Repeated Measured Mixed Model for qHBsAg,	mITT Population	Yes	
	HBV DNA, HBcrAg and pg-RNA levels: Days 85			
	and 169			
14.2.2.4.1	Summary and change from baseline of IFN-γ	mITT Population	Yes	
	frequency by ELISpot assay in PBMCs: Days 85			
	and 169			
14.2.2.4.2	Non-Parametric Model for IFN-γ frequency by	mITT Population	Yes	
	ELISpot assay in PBMCs: Days 85 and 169			
14.3. Safety Da	ta Summary Tables			
14.3.1. Adverse	Events			

22-Apr-2024

TFL Number	Title	Analysis Set	Included in	TOP LINE
			Final report	TABLES
14.3.1.1	Overall Summary of Treatment Emergent Adverse	Safety Population	Yes	V
	Events			
14.3.1.2	TEAEs by System Organ Class and Preferred	Safety Population	Yes	
	Term			
14.3.1.3	TEAEs by Preferred Term	Safety Population	Yes	
14.3.1.4	TEAEs related to study drug by System Organ	Safety Population	Yes	
	Class and Preferred Term			
14.3.1.5	TEAEs related to study drug Grade 3 or higher by	Safety Population	Yes	
	System Organ Class and Preferred Term			
14.3.1.6	TEAEs by maximum severity by System Organ	Safety Population	Yes	
	Class and Preferred Term			
14.3.2 Serious	Adverse Events		·	
14.3.2.1	Serious TEAEs by System Organ Class and	Safety Population	Yes	
	Preferred Term			
14.3.2.2	TEAEs leading to study drug permanently	Safety Population	Yes	
	discontinued by System Organ Class and			
	Preferred Term			
14.3.3 Other Ad	lverse Events		·	
14.3.3.1.1	Medically-Attended AEs (MAEs) by System Organ	Safety Population	Yes	
	Class and Preferred Term. Treatment Period			
14.3.3.1.2	Medically-Attended AEs (MAEs) by System Organ	Safety Population	Yes	
	Class and Preferred Term. Follow-Up Period			
14.3.3.2.1	New-onset Chronic Illnesses (NCIs) by System	Safety Population	Yes	
	Organ Class and Preferred Term. Treatment			
	Period			
14.3.3.2.2	New-onset Chronic Illnesses (NCIs) by System	Safety Population	Yes	
	Organ Class and Preferred Term. Follow-Up			
	Period			

TFL Number	Title	Analysis Set	Included in Final report	TOP LINE TABLES
14.3.3.3.1	Immune-mediated Medical Conditions (IMCs) by System Organ Class and Preferred Term. Treatment Period	Safety Population	Yes	
14.3.3.3.2	Immune-mediated Medical Conditions (IMCs) by System Organ Class and Preferred Term. Follow- Up Period	Safety Population	Yes	
14.3.4 Clinical I	_aboratory Tests			
14.3.4.1.1	Summary of pre-dose Values and Change from baseline for Clinical Laboratory Hematology Results	Safety Population	Yes (Through D169)	
14.3.4.1.2	Summary of Abnormalities for Clinical Laboratory Hematology Results	Safety Population	Yes (Through D169)	
14.3.4.1.3	Summary of Clinical Laboratory Hematology Results: Shift from baseline vs post-baseline category	Safety Population	Yes (Through D169)	
14.3.4.2.1	Summary of pre-dose Values and Change from baseline for Clinical Laboratory Biochemistry Results	Safety Population	Yes (Through D169)	
14.3.4.2.2	Summary of Abnormalities for Clinical Laboratory Biochemistry Results	Safety Population	Yes (Through D169)	
14.3.4.2.3	Summary of Clinical Laboratory Biochemistry Results: Shift from baseline vs post-baseline category	Safety Population	Yes (Through D169)	
14.3.4.3.1	Summary of pre-dose Values for Continuous Urinalysis Results	Safety Population	Yes	
14.3.4.3.2	Summary of Values for Categorical Urinalysis Results	Safety Population	Yes	

TFL Number	Title	Analysis Set	Included in	TOP LINE
			Final report	TABLES
14.3.4.3.3	Summary of Abnormalities for Clinical Laboratory	Safety Population	Yes	
	Urinalysis Results			
14.3.4.3.4	Summary of Clinical Laboratory Urinalysis Results:	Safety Population	Yes	
	Shift from baseline vs post-baseline category			
14.3.5 Reactoger	-			
14.3.5.1	Incidence of Reactogenicity Events	Safety Population	Yes	
14.3.6 Hepatitis F	Flares			
14.3.6.1	Incidence of Hepatitis Flares	Safety Population	Yes	
14.3.6.2	Summary of patients achieving HBsAg loss by Hepatitis Flares	Safety Population	Yes	
14.3.6.3	Logistic Regression Analysis for HBsAg loss by Hepatitis Flares at Day 169	Safety Population	Yes	
14.3.7 Vital Signs	5		,	I
14.3.7.1	Summary of Values and Change from baseline for Vital Signs: Results by Visit	Safety Population	Yes (Through D169)	
14.3.7.2	Summary of Values and Change from pre-dose for Vital Signs: Results after first and second dose	Safety Population	Yes (Through D169)	
14.3.7.3	Summary of Height, weight, and BMI change from baseline	Safety Population	Yes (Through D169)	
14.3.8 Electrocar	diogram Measurements (12-Lead ECG)			
14.3.8.1	Summary of Evaluation for 12-Lead ECG Results	Safety Population	Yes (Through D169)	
14.3.9 Physical E	xamination		,	
14.3.9.1.1	Complete Physical Examination after Baseline (Day 169/ET)	Safety Population	Yes	
14.3.9.1.2	Targeted and symptom-driven Physical Examination after Baseline	Safety Population	Yes (Through D169)	
Listing Number	Examination and Basonile			
16.2.1 Patient's D	Disposition			

22-Apr-2024

TFL Number	Title	Analysis Set	Included in	TOP LINE
			Final report	TABLES
16.2.1.1	Listing of Patient's Disposition and Status	All Patients in DB	Yes	
16.2.1.2.1	Listing of Eligibility Criteria	All Patients in DB	Yes	
16.2.1.2.2	Listing of Eligibility Criteria for Next Dose	All Patients in DB	Yes	
16.2.1.3	Listing of Screen Failure Patients	Screening Failure Patients	Yes	
16.2.1.4	Listing of Analysis Populations	All Patients in DB	Yes	
16.2.2 Protocol	Deviations			
16.2.2.1	Listing of Protocol Deviations	Randomized Patients	Yes	
16.2.3 Patients	excluded from Efficacy Analyses			1
16.2.3.1	Listings of Patients excluded from Efficacy	mITT Population	Yes	
	analyses			
16.2.4 Demogra	phic and Baseline Characteristics			
16.2.4.1	Listing of Demographic Characteristics	All Patients in DB	Yes	
16.2.4.2	Listing of Liver Biopsy and Fibroscan	All Patients in DB	Yes	
16.2.4.3	Listing of Hepatitis B Genotyping, HCV, HDV and	All Patients in DB	Yes	
	HIV tests			
16.2.4.4	Listing of Medical History by Patient and MedDRA	All Patients in DB	Yes	
	System Organ Class and Preferred Term			
16.2.4.5	Listing of Prior and Concomitant (and Post-	All Patients in DB	Yes	
	Treatment) Medication			
16.2.5 Study Dr	ug Exposure for Investigational Products			•
16.2.5.1	Study Treatment Completion	All Patients in DB	Yes	
16.2.5.2	Listing of Study Drug Administration	All Patients in DB	Yes	
16.2.5.3	Listing of Study Drug Dispensation	All Patients in DB	Yes	
16.2.5.4	Patient Randomization Listing	Randomized Patients	Yes	
16.2.6 Efficacy	Data			·
16.2.6.1	Listing of Serology and Viral markers	Randomized Patients	Yes	

TFL Number	Title	Analysis Set	Included in	TOP LINE
			Final report	TABLES
16.2.6.2	Listing of IFN-γ frequency by ELISpot assay	Randomized Patients	Yes	
16.2.7 Adverse	Events		.	.
16.2.7.1	Listing of Adverse Events	All Patients in DB	Yes	
16.2.7.2	Listing of Serious Adverse Events	All Patients in DB	Yes	
16.2.7.3	Listing of TEAEs leading to Study Drug Discontinuation or Study Discontinuation	All Patients in DB	Yes	
16.2.7.4	Listing of Study-Drug Related TEAEs	All Patients in DB	Yes	
16.2.7.5	Listing of Medically-Attended AEs (MAEs)	All Patients in DB	Yes	
16.2.7.6	Listing of New-onset Chronic Illnessess (NCIs)	All Patients in DB	Yes	
16.2.7.7	Listing of Immune-mediated Medical Conditions (IMCs)	All Patients in DB	Yes	
16.2.8 Clinical	Laboratory Tests			
16.2.8.1	Listing of Clinical Laboratory Hematology Results	All Patients in DB	Yes	
16.2.8.2	Listing of Clinical Laboratory Biochemistry Results	All Patients in DB	Yes	
16.2.8.3	Listing of Clinical Laboratory Urinalysis Results	All Patients in DB	Yes	
16.2.8.4	Listing of Clinical Laboratory tests: Pregnancy Test Results	All Patients in DB	Yes	
16.2.8.5	Listing of Clinical Laboratory tests: Urine drug and alcohol screen	All Patients in DB	Yes	
16.2.9 Reactog	enecity Events	1		-
16.2.9.1	Listing of Diary Card and Reactogenicity Events	All Patients in DB	Yes	
16.2.10 Hepatit	is Flares	1		1
16.2.10.1	Listing of Hepatitis Flares	All Patients in DB	Yes	
16.2.11 Vital Si	gns			,
16.2.11.1	Listing of Vital Signs and Height, weight, and BMI	All Patients in DB	Yes	
16.2.12 Electro	cardiogram Measurements (12-Lead ECG)			,
16.2.12.1	Listing of 12-Lead ECG measurements	All Patients in DB	Yes	
				•

TFL Number	Title	Analysis Set	Included in	TOP LINE	
			Final report	TABLES	
16.2.13 Physical	16.2.13 Physical Examinations				
16.2.13.1	Listing of Physical Examinations	All Patients in DB	Yes		

Addendum to the Statistical Analysis Plan

Study ALT-301-201, ALT-301-202 Phase 2, Double-blind, Randomized, Placebo-controlled Study of HepTcell (Adjuvanted FP-02.2) as an Immunotherapeutic Vaccine in Treatment-naïve Patients with Inactive Chronic Hepatitis B

An interim analysis was conducted at Week 24 that demonstrated that the primary and secondary endpoints of the study were not met. HepTcell was well-tolerated, with no significant safety events.

Per protocol Section 7.2, the Sponsor is terminating the study for lack of efficacy. The IND and respective CTAs will be inactivated, and the investigational product will not undergo further clinical testing. As there were no ongoing MAEs, NCIs or IMCs at the time of termination, safety follow-up will end as of this date. Any accrued efficacy or safety information prior to study termination will be provided in tables and listings only up through the date of study termination.

The following tables and listings will be generated to supplement those that were produced for the Week 24 interim analysis:

14.3.3 Othe	r Adverse Events	
14.3.3.1.2	Medically-Attended AEs (MAEs) by System Organ	Safety
	Class and Preferred Term. Follow-Up Period	Population
14.3.3.2.2	New-onset Chronic Illnesses (NCIs) by System	Safety
	Organ Class and Preferred Term. Follow-Up Period	Population
14.3.3.3.2	Immune-mediated Medical Conditions (IMCs) by System Organ Class and	Safety
	Preferred Term. Follow-	Population
	Up Period	

Listing Number				
16.2.1 Patient's Dis	sposition			
16.2.1.1	Listing of Patient's Disposition and Status	All Patients in DB		
16.2.1.2.1	Listing of Eligibility Criteria	All Patients in DB		
16.2.1.2.2	Listing of Eligibility Criteria for Next Dose	All Patients in DB		
16.2.1.3	Listing of Screen Failure Patients	Screening Failure		
		Patients		
16.2.1.4	Listing of Analysis Populations	All Patients in DB		
16.2.2 Protocol De	16.2.2 Protocol Deviations			
16.2.2.1	Listing of Protocol Deviations	Randomized Patients		

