3.4. Safety Endpoints

- Incidence and severity of AEs, medically-attended AEs (MAEs), new-onset chronic illnesses (NCIs), and immune-mediated medical conditions (IMCs)
- Incidence and severity of local and systemic reactogenicity events
- Incidence and duration of hepatitis flares, defined as alanine aminotransferase (ALT) \geq 3 × upper limit of normal (ULN) and \geq 100 U/L
- Changes in ALT, aspartate aminotransferase (AST), alkaline phosphatase (AP), gamma glutamyl transferase (GGT), bilirubin total and direct, international normalized ratio (INR) and other laboratory parameters

Safety endpoints will be assessed separately for the 24-week Treatment Period and 52-week Follow-Up Period.

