10.4.3. Analysis of Safety

Quantitative safety data will be summarized using descriptive statistics and frequency distributions. Qualitative safety data will be summarized by frequencies and percentages. All summaries will be presented by treatment arm. AEs will be coded using Medical Dictionary for Regulatory Activities (MedDRA) and concomitant medications will be coded using WHO drug dictionary.

Laboratory evaluations, vital signs assessments and ECG parameters will be summarized by treatment group and protocol specified collection time point. A summary of change from baseline at each protocol specified time point by treatment group will also be presented.

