Safety endpoints that are also measured during the Follow-Up period will be assessed separately for the 24-week Treatment Period and 52-week Follow-Up Period.

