5.3.3.12 Laboratory Evaluation

Hematology (including white blood cells (WBC), red blood cells, hemoglobin, hematocrit, mean corpuscular volume, mean corpuscular hemoglobin, mean corpuscular hemoglobin concentration, platelets, WBC differential (absolute and %), neutrophils, lymphocytes, monocytes, eosinophils, basophils); Liver Panel (including total and direct bilirubin, AST, ALT, total protein, albumin, GGT, lactate dehydrogenase, AP, INR); Serum Chemistry (including sodium, potassium, urea, creatinine, calcium, phosphate, glucose, creatine kinase) will be evaluated at each scheduled visit day during treatment period, as well as the scheduled days during Treatment follow-up period.

Urinalysis (including protein, bilirubin, urobilinogen, ketones, glucose, leukocyte esterase, red blood cells, pH, nitrites, specific gravity, microscopy) will only be evaluated in the same days during treatment period but not during the Treatment follow-up period.

The summary statistics (including number, mean, SD, median, Q1, Q3, minimum, and maximum) of all quantitative laboratory variables (laboratory values and changes from baseline) will be calculated for each dose during the treatment period and for each visit during the follow-up period, by treatment arm.

Laboratory data will be analyzed at pre-doses of Dose 1 to 6. For all parameters, the last available measurement after last dose and before the current dose will be the representative value to be summarized for each dose (ie: for dose 2, last value taken from "Date of dose 1 + 1 day until Date of dose 2").

For each visit during the follow-up period, the last of all measurements for the corresponding visit will be the representative value to be summarized.

The number (%) of patients with abnormal results (out of normal range) for each of the laboratory variables will be summarized at pre-dose of Doses 1 to 6 and in each visit during the follow-up period and treatment arm

22-Apr-2024

Shift tables for baseline versus each pre-dose for Doses 1 to 6 and follow-up visits will be presented for the hematology, urinallysis and chemistry laboratory parameters.

Data collected for Microscopy in Urinalysis (if clinically indicated or hemoglobin is detected on dipstick) will only be listed.

Data will be listed by patient.

Only available data will be used, and missing data will not be imputed.

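### The SAP text requires by-arm laboratory summaries at follow-up visits, but its table index stops all six hematology and biochemistry tables at Day 169 and the Addendum adds none

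*SAP*

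**What the plan says.** **Protocol.** Section 3.4 names changes in ALT, AST, AP, GGT, total and direct bilirubin, INR and other laboratory parameters as a safety endpoint. It adds: "Safety endpoints will be assessed separately for the 24-week Treatment Period and 52-week Follow-Up Period". Section 10.4.3 states: "Laboratory evaluations, vital signs assessments and ECG parameters will be summarized by treatment group and protocol specified collection time point". Table 2 schedules hematology, serum chemistry and a liver panel at all four follow-up visits: Days 232, 323, 414 and 505.

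**SAP text (version 2.0).** Section 4.3 repeats the period rule: "Safety endpoints that are also measured during the Follow-Up period will be assessed separately for the 24-week Treatment Period and 52-week Follow-Up Period". Section 5.3.3.12 then makes three commitments:

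- Summary statistics for values and changes "will be calculated for each dose during the treatment period and for each visit during the follow-up period, by treatment arm".
- Counts of abnormal results, which "will be summarized at pre-dose of Doses 1 to 6 and in each visit during the follow-up period and treatment arm".
- "Shift tables for baseline versus each pre-dose for Doses 1 to 6 and follow-up visits will be presented".

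**SAP index and Addendum.** In the column for the final report, Appendix 1 marks the three hematology tables (14.3.4.1.1 to 14.3.4.1.3) and the three biochemistry tables (14.3.4.2.1 to 14.3.4.2.3) "Yes (Through D169". The Addendum says: "The following tables and listings will be generated to supplement those that were produced for the Week 24 interim analysis". The tables it then lists are the follow-up versions for MAEs, NCIs and IMCs. Hematology and biochemistry appear only as Listings 16.2.8.1 and 16.2.8.2.

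**The concern.** The SAP gives two different instructions for the same output. A programmer working from 5.3.3.12 would produce follow-up laboratory tables by arm. A programmer working from Appendix 1 and the Addendum would not. The index and Addendum define what is delivered, so the likely result is that the follow-up part of a named safety endpoint has no by-arm summary.

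The liver tests give this its weight. HepTcell is designed to direct T-cell immunity against HBV (Protocol 1.1.2), and the protocol builds its laboratory monitoring around hepatitis flares and liver-function abnormalities (Protocol 4.3). Whether ALT, bilirubin or INR moved differently between arms after dosing ended is a question the four follow-up liver panels were scheduled to answer.

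**Working it through.** There is no sample-size, power or error-rate figure to reproduce. The check sets the passages side by side and counts.

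1. **Requirement.** Protocol 3.4 and SAP 4.3 require assessment of the follow-up period. Protocol 10.4.3 requires laboratory summaries by treatment group at each collection time point. SAP 5.3.3.12 turns this into three table types: summaries, abnormality counts and shifts. All four passages are current text.

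2. **Planned output.** Three table types × two laboratory groups = 6 tables in the index, and 6 of 6 carry the Day 169 limit. The urinalysis tables do not carry it, which causes no conflict because 5.3.3.12 does not evaluate urinalysis in follow-up. The index has no separate liver-panel table, so I take the liver tests to fall under biochemistry.

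3. **Scheduled data left untabulated.** Four follow-up visits have hematology, chemistry and liver-panel draws. The planned window is 505 − 169 = 336 days, or 336/7 = 48 weeks. Planned time after Day 1 is 505 − 1 = 504 days, so the window is 336/504 = 67% of it. This describes the schedule. Termination shortened what was collected by an amount the documents do not give.

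4. **Could another table fill the gap?**
   - *Flares:* SAP 4.3 and 5.3.3.8 limit the flare analysis to the treatment period.
   - *Adverse events:* after Day 169 only MAEs, NCIs and IMCs are recorded (Protocol 8.3.2). A liver abnormality that qualifies as one of these is tabulated by arm. A rise seen on a scheduled panel that does not qualify enters no by-arm table.
   - *Listings:* 16.2.8.1 and 16.2.8.2 show individual values without a summary.

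5. **Is the change declared?** SAP 5.3.17 lists one departure from the protocol, the uncollected ECG parameters. The version history says the tables, figures and listings were modified in line with the Addendum. Neither it nor the Addendum mentions the laboratory cut or gives a reason specific to it.

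6. **Does the termination text settle it?** SAP section 2 and the Addendum say accrued efficacy and safety information will be given in tables and listings up to the termination date. Protocol 10.5 likewise has safety endpoints, as applicable, reported on all data accrued to each database lock. Both point towards tabulating the follow-up laboratory data that exist.

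**The case against.** The strongest defence is that the cut is deliberate and follows from termination. The Week 24 interim analysis missed the primary and secondary endpoints, development is ending, and safety follow-up stops. The Addendum itemises the extra outputs, and an itemised list can be read as controlling over a general sentence about tables and listings. The same Day 169 label appears on the tables for vital signs, height/weight/BMI, ECG and targeted physical examination. Protocol 10.6 lets the SAP supersede the protocol for analyses other than the primary. Laboratory safety was only ever descriptive, so no formal test is lost.

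Much of this stands. It explains the cut, and it answers a stronger inference that a reader might draw: that liver results were singled out to hide a signal. The documents do not support that, because the label is spread across several safety domains and the individual laboratory values are still listed.

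A reader might also infer that nothing at all can be said between arms. That goes too far. SAP 5.3 says listings are generally sorted by treatment arm, so with about 80 patients counts could be made by hand. The by-arm MAE, NCI and IMC tables remain, and SAP 5.3.12 schedules a DMC meeting at the conclusion of the trial.

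The defence does not remove the conflict. Protocol 10.6 resolves a difference between protocol and SAP, whereas here the SAP disagrees with itself. For vital signs and ECG, the SAP's own text (5.3.3.11 and 5.3.3.10) also stops at Day 169 or end of treatment. For laboratory data the text goes on to follow-up and the index does not.

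**Conclusion.** The inconsistency is real and sits in the current SAP. Following the index and Addendum, all six hematology and biochemistry tables end at Day 169. Follow-up changes in ALT, AST, AP, GGT, bilirubin and INR, scheduled at four visits, then reach the report only as by-patient listings. What is lost is a planned by-arm summary. Individual data are kept, and liver events qualifying as MAE, NCI or IMC are still compared descriptively.

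This should be corrected, but it does not bear on the primary efficacy conclusion. It rests on two readings: that the liver panel is reported under biochemistry, and that the Day 169 label means what it says.

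A reader might try to estimate from the planned 24-month enrolment what share of patients had reached Day 505 by termination. The documents give neither enrolment dates nor a termination date, and the answer depends heavily on the enrolment pattern and lag assumed, so no percentage should be stated.

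**What to change.** Remove the Day 169 restriction from Tables 14.3.4.1.1 to 14.3.4.2.3 in Appendix 1 and add the six tables to the Addendum. At minimum, do this for the biochemistry and liver-panel tables, 14.3.4.2.1 to 14.3.4.2.3. Report Days 232, 323, 414 and 505 on data accrued to termination, and show the number of patients with a result at each visit in each arm.

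If the sponsor keeps the cut, 5.3.3.12 and 5.3.17 should say that follow-up laboratory data are listed only, and why. That makes the SAP consistent but leaves the by-arm summary missing.

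The cost is some extra programming. The analyses are already specified in 5.3.3.12 and the values are already being listed. However, Tables 14.3.4.1.1 and 14.3.4.2.1 are titled as pre-dose summaries, so titles and visit handling may need work. Numbers at later visits will be incomplete because of termination, which the per-visit counts will make visible.
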